4. JUSTIFICATION FOR CLINICAL INVESTIGATION DESIGN PLAN

Approximately 60 million individuals worldwide suffer from atrial fibrillation, which is the most common type of cardiac arrhythmia.⁽¹⁾ Patients with atrial fibrillation have approximately a 4-fold increased risk of mortality compared to the general population.⁽³⁾ In addition to increased risk of death, atrial fibrillation also increases the risk of heart failure and stroke. The imminent risks of stroke can be mitigated with prompt administration of anticoagulants, which relies on timely diagnosis of atrial fibrillation.^(4, 5)

Certain populations are more vulnerable to atrial fibrillation than others; studies have indicated that risk factors for increased risk include older age, sedentary lifestyle, obesity, diabetes mellitus, thyroid disease, obstructive sleep apnea, hypertension, myocardial infarction, heart failure, smoking, and alcohol.^(2, 6) Detecting atrial fibrillation in its early stages can significantly reduce the high disability and mortality rate. A study reviewing the prevalence of atrial fibrillation in 2009 estimated that 700,000 cases were undetected, comprising 13.1% of all cases; half of these projected cases of undiagnosed atrial fibrillation were at increased susceptibility to stroke.⁽⁷⁾

The standard for diagnosis of atrial fibrillation is use of an electrocardiogram (ECG); advancement of this technology, especially via wearable technology, for early detection can improve the prognosis for patients and enable them to seek medical care before the arrhythmia progresses into more adverse complications. Prior studies have demonstrated usability and performance of wrist-wearable ECG spot check devices in the detection of atrial fibrillation.⁽⁸⁾ This study is designed to validate the performance of Masimo INVSENSOR00057 ECG module in detecting atrial fibrillation in adults with persistent or paroxysmal atrial fibrillation who are in atrial fibrillation.

Study Title: Validation of the performance of the electrocardiogram (ECG) function of the Masimo INVSENSOR00057

5. BENEFITS AND RISKS OF THE STUDY DEVICES, CLINICAL PROCEDURE, AND CLINICAL INVESTIGATION

5.1. Anticipated Clinical Benefits

There will be no direct benefit to the enrolled subjects. This is a validation study to support regulatory submission for a new wrist-wearable ECG technology, which may enable users to identify potential life-threatening conditions more appropriately.

5.2. Anticipated Adverse Events

The following adverse events are anticipated:

5.2.1. Risks Associated with the Study Devices

The noninvasive devices used in this study are similar in technology and design to commercially available FDA-cleared devices and hence pose minimal risk to subjects. There is a risk of temporary discomfort to subjects at placement locations, including temporary skin irritation. If the device is worn too tight around the wrist, there is potential for a pressure injury. In the absence of intact skin (e.g., cuts or abrasions) at or near the application site, the subject will be disqualified from the study to avoid potential discomfort.

5.2.2. Risks Associated with Participation in the Clinical Investigation

5.2.3. Risks Associated with Placement of FDA-cleared 12-lead ECG Electrodes

Subjects may be asked to use an alcohol pad or fingertip abrasive pad on application sites of the FDA-cleared 12-lead ECG electrodes to allow the electrodes to adhere to the skin. Risks associated with skin preparation include cuts and/or abrasions, rash, itching skin, flushing or redness of the skin, unusually warm skin, skin inflammation, and/or skin irritation. Each of these discomforts are temporary and should fade over time.

Subjects may also be asked to shave the site of application of the FDA-cleared 12-lead ECG electrodes application to allow the sensors to adhere to the skin. Risks associated with shaving include cuts and/or abrasions, bleeding, infection, razor burn, rash, itching skin, flushing or redness of the skin, unusually warm skin, skin inflammation, skin irritation, ingrown hairs, and/or inflamed hair follicles. While some of these symptoms may last up to several days after shaving, discomforts are temporary and should fade over time. Subjects have the option to decline shaving the electrode application sites in the informed consent. Moreover, subjects can stop these measures at any time if they feel uncomfortable.

5.2.4. Risks from Inflicted Knowledge

The risk of inflicted knowledge will be reduced by assuring the subjects that device readings are for research use only. In the case that a subject becomes aware of a condition (arrhythmia, etc.) during the study, study staff will recommend that they contact their primary care physician, and will document this recommendation.

5.2.5. Risks Associated with Study Data

The other main risk associated with the study is a potential breach of confidentiality which will be minimized by limiting the collection of protected health information (PHI) and through secure data storage practices.

CLINICAL INVESTIGATION PLAN

Study Title: Validation of the performance of the electrocardiogram (ECG) function of the Masimo INVSENSOR00057

6. OBJECTIVES OF THE CLINICAL INVESTIGATION

The objective of this study is to validate the performance of the ECG function of the Masimo INVSENSOR00057 against contemporaneous measurements from reference 12-lead ECG gold standard. Study endpoints are as follows:

Primary: Evaluate the performance of ECG rhythm classification and waveform characteristics.

- Sensitivity and specificity of the automatic classification of atrial fibrillation (AFib) and normal sinus rhythm (NSR) by the single-lead ECG module of INVSENSOR00057 against clinical interpretation of reference 12-lead ECG.

7. DESIGN OF THE CLINICAL INVESTIGATION

7.1. General

This is a prospective validation study of Masimo INVSENSOR00057 ECG function (see [Appendix I](#) for a study workflow) in a mix of subjects with and without a diagnosis of AFib. Enrolled subjects will receive [REDACTED]

[REDACTED] on Masimo INVSENSOR00057. [REDACTED]

[REDACTED] Clinician interpretation of reference 12-lead ECG classification will be used in classifying subjects to rhythm cohorts and establish the basis for analysis of subject data with respect to study endpoints.

7.3. Definition of Completion of the Clinical Investigation

The study will be considered complete when quality data from [REDACTED] subjects have been collected and evaluated.

7.4. Study Device(s)

Masimo devices:

- Masimo INVSENSOR00057 – Investigational

Comparators:

- FDA-approved 12-lead electrocardiogram (ECG) electrodes and monitors

Research Equipment:

Data collection research equipment [REDACTED]

7.5. Subjects

7.5.1. Inclusion Criteria

- Subject is 22 years of age or older.
- Subject is comfortable to read and communicate in English*.
- Subject belongs to one of the two groups:
 - Subjects without prior arrhythmia diagnosis presenting in normal sinus rhythm (Group 1)
 - Subjections with history of paroxysmal or persistent atrial fibrillation presenting in atrial fibrillation (Group 2).

*This is to ensure the subject can provide informed consent (as Masimo INVSENSOR00057 ECG study materials are currently available in English only) and can comply with study procedures.

7.5.2. Exclusion Criteria

- Subjects who are physically unable to wear a wristwatch.
- Subjects whose skin is not intact (e.g., has open wounds, has inflamed tattoos or piercings, has visible healing wounds) in or at the vicinity of the device placement site.
- Subjects with an implantable defibrillator or cardiac pacing device.
- Subjects with a skin condition which would preclude proper ECG electrode placement.
- Subjects with known allergic reactions to adhesive tapes or ECG gel.
- Subjects previously diagnosed with lethal cardiac arrhythmia, determined by the investigator.
- Subjects not suitable for the investigation at the discretion of the investigator or the clinical team.

Study Title: Validation of the performance of the electrocardiogram (ECG) function of the Masimo INVSENSOR00057

7.5.3. Number of Subjects

7.5.4. Subject Classifications

Subjects will be classified according to the criteria below:

- **Screened** – Subjects who are assessed for study eligibility.
- **Enrolled** – Subjects who have met all the inclusion criteria, do not meet any exclusion criteria, and have been assigned a subject identification number.
- **Screen Failure** – Subjects who do not meet all the eligibility criteria. (Reason for the subject's ineligibility will be documented on a *Screening and Enrollment Log*).
- **Withdrawn** – Subjects who do not complete the study due to reasons listed below:
 - Subject voluntarily opts not to participate.
 - Subject was discontinued from study at the discretion of the clinical team.
- **Completed** – Subjects with a completed simultaneous ECG measurement using Masimo INVSENSOR00057 and interpretable 12-lead reference ECG.

7.5.5. Study Duration

The study is anticipated to require ~3 months to complete. Subject participation in the study will be approximately 30 minutes.

7.6. Study Procedures

7.6.1. Subject Recruitment and Pre-screening

Subjects with no known arrhythmia (normal sinus rhythm) will be recruited at [REDACTED] and subjects with known diagnosis of atrial fibrillation will be recruited at external sites from medical clinics or cardiology offices. Subjects in the AFib cohort may have paroxysmal, persistent, or permanent forms of AFib, and will be determined by the referring cardiologist to be in atrial fibrillation at the time of routine office visit.

7.6.2. Informed Consent and Screening

Following the identification of a potential eligible subject as defined by the inclusion and exclusion criteria, the subject will be informed about the purpose of the study and given an overview of the study procedures. Study staff will explain the potential risks and benefits, and discuss the subject's rights and privacy information. Subjects will be provided with ample time to review the consent form and ask questions. The research team will emphasize that participation is voluntary and declining participation in the study will not result in any penalty or loss of benefits that the subject is otherwise entitled.

Once the subject's questions have been answered and the consent documents are signed and dated, the Principal Investigator or delegate will also sign the informed consent documents, approving the subject to be enrolled in the study. The investigator shall retain the original copy of the signed informed consent documents in each subject's records and provide a copy to the subject. No study related activities shall be conducted until the consent form is signed.

Study Title: Validation of the performance of the electrocardiogram (ECG) function of the Masimo INVSENSOR00057

Subjects will be screened to determine eligibility for study enrollment. Subjects must meet all inclusion criteria and none of the exclusion criteria to participate in the study. All subjects screened will be documented on the *Screening and Enrollment Log*. Subjects who do not meet the eligibility criteria will be considered screen failures and the reason for the status of screen failure will be documented on the *Screening and Enrollment Log*.

Information on subject demographics, medical history including comorbidities and concurrent medications will be collected (see [Appendix II](#)).

7.6.3. Study Procedures

7.6.3.1. ECG Measurements

The Masimo INVSENSOR00057 placed on the wrist according to the *Investigator Brochure (IB)*. Site staff will check proper application of wrist strap. Next, the reference 12-lead ECG electrodes will be placed. INVSENSOR00057 will be paired via Bluetooth connection [REDACTED]

The subjects will be provided with assistance with INVSENSOR00057 placement according to the user manual [REDACTED] Once the subject is familiarized with the device, study measurement commences.

The on-site trained research personnel will confirm the ECG recordings are of diagnostic quality prior to removing the electrodes. At the conclusion of the procedure, the 12-lead ECG electrodes and INVSENSOR00057 will be removed.

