An atrial fibrillation ECG classification will indicate that ECG shows signs of irregular heartbeat. Atrial fibrillation is the most common pathologic cardiac arrhythmia. Masimo INVSENSOR00057 can detect signs of atrial fibrillation between heart rates of 50 to 150 bpm. Atrial fibrillation can often be accompanied by a rapid heart rate. Subjects who have not been previously diagnosed with atrial fibrillation and consistently receive this result or subjects who are not feeling well should consult with their healthcare provider. The resulting output does not guarantee the presence or absence of atrial fibrillation or other arrhythmias.

- Inconclusive

An Inconclusive ECG classification indicates that the ECG recording could not be classified, which may be due to a number of reasons such as other arrhythmias, pacing, or heart conditions that Masimo INVSENSOR00057

Study Title: Validation of the performance of the electrocardiogram (ECG) function of the Masimo INVSENSOR00057

is not designed to detect. It is recommended to repeat the measurement in a few minutes for subjects who get this result. An inconclusive classification does not indicate the presence or absence of any arrhythmias (including AFib) or other heart conditions. Subjects who consistently receive this result should follow up with their healthcare provider, particularly if they are feeling unwell.

- Noise

This classification of the ECG means the ECG waveform quality and performance were compromised and the device cannot report any measurements from the ECG.

INVSENSOR00057 Heart Rate Classification:

- Low Heart Rate

A low heart rate ECG classification will indicate a heart rate lower than 50 bpm, which can be commonly due to benign causes such as certain medication effects, or a normal finding during rest in particular among well-conditioned athletes or other cardiovascularly-fit individuals. However, subjects who are not feeling well should follow up with their healthcare provider as sometimes very low heart rates can indicate an underlying cardiovascular condition.

- High Heart Rate

A high heart rate ECG classification will indicate heart rates greater than 100 bpm, which can be due to exercise, stress, the presence of cardiac arrhythmia, or consumption of alcohol, stimulants or caffeinated drinks. Subjects who are not feeling well should follow up with their healthcare provider.

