8. STATISTICAL DESIGN AND ANALYSIS

The study objective is to evaluate the performance of the INVSENSOR00057 rhythm classification and waveform characteristics relative to a 12-lead ECG. The INVSENSOR00057 evaluates a 30 second duration, single lead, ECG waveform measurement. One of four possible outcomes for each measurement per Table 8a.

Outcome	Description
AFib	Waveform is classified as atrial fibrillation
NSR	Waveform is classified as Normal Sinus Rhythm
Inconclusive	INVSENSOR00057 cannot determine the rhythm classification
Noise	INVSENSOR00057 has determined that the waveform is too noisy and does not represent a physiological signal

CLINICAL INVESTIGATION PLAN

Study Title: Validation of the performance of the electrocardiogram (ECG) function of the Masimo INVSENSOR00057

Data from subjects where reference 12-lead ECG did not provide readable ECG waveforms (as assessed by medical personnel) will be excluded from the primary analysis.

[figure not shown]

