8.1. Classification Accuracy Calculations

8.1.1. Data Analysis

Classification accuracy will be measured on all measurements where both the INVSENSOR00057 and the 12-lead reference ECG provided a classification of either AFib or NSR. (This incidence rate of Inconclusive and Noise outcomes on the INVSENSOR00057 will be evaluated separately.) Sensitivity is the probability that the diagnostic test is positive for the disease, given that the subject actually has AFib, while specificity is the probability that the diagnostic test is negative, given that the subject does not have AFib (or conversely, has NSR).

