8.1.2. Sample Size Justification

Sample size was determined to meet simultaneous requirements for both sensitivity and specificity analysis. The PASS 2019¹ software package was used to calculate the appropriate sample size using the “Confidence Intervals for One-Sample Sensitivity and Specificity” module.

¹ PASS 2019 Power Analysis and Sample Size Software (2019). NCSS, LLC. Kaysville, Utah, USA, ncss.com/software/pass.

Study Title: Validation of the performance of the electrocardiogram (ECG) function of the Masimo INVSENSOR00057

[REDACTED]

[REDACTED]

[REDACTED]

[REDACTED]

[REDACTED]

[REDACTED]

[REDACTED]

[REDACTED]

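### Could an on-site quality check let staff repeat watch recordings until they classify, hiding device failures and narrowing the confidence intervals?

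*Combined protocol and SAP*

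**What the plan says.** Section 7.6.3.1 puts the watch on the wrist, then places the reference 12-lead electrodes, takes the measurement, and adds: "The on-site trained research personnel will confirm the ECG recordings are of diagnostic quality prior to removing the electrodes". It then names the 12-lead electrodes and the watch separately as the items removed.

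The introduction to Section 8 gives the watch "One of four possible outcomes for each measurement per Table 8a": AFib, NSR, Inconclusive or Noise. Section 8.1.1 defines which recordings count towards accuracy: "Classification accuracy will be measured on all measurements where both the INVSENSOR00057 and the 12-lead reference ECG provided a classification of either AFib or NSR". It adds: "This incidence rate of Inconclusive and Noise outcomes on the INVSENSOR00057 will be evaluated separately".

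Section 7.5.4 defines completed subjects as "Subjects with a completed simultaneous ECG measurement using Masimo INVSENSOR00057 and interpretable 12-lead reference ECG". Section 7.3 begins "The study will be considered complete when quality data from", and the number of subjects that follows is blacked out. Section 8.1.2 names the PASS module "Confidence Intervals for One-Sample Sensitivity and Specificity"; its inputs and results are blacked out.

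The only visible mention of repeating is in the device description in Section 3, about an Inconclusive result: "It is recommended to repeat the measurement in a few minutes for subjects who get this result".

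**The concern.** A quality check made while the electrodes are still attached is useful mainly because a poor recording can be taken again. The sentence does not say which recordings it covers, what the criterion is, or what follows a failed check. If it covers the watch, it overlaps with the device's own Noise outcome, and Section 3 tells users to repeat after Inconclusive.

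Two harms would then be possible. First, Noise and Inconclusive are device failures that Section 8.1.1 evaluates as a result. Because sensitivity and specificity are conditional on a classified recording, that failure rate is what shows the reader how many hard recordings were left out. Repeats triggered by failure could make it look better than it is. Second, the unit of analysis is the measurement, while the planning method is a one-sample binomial one. If some subjects contributed several classified recordings, intervals that ignore this would be too narrow.

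**Working it through.** The plan has no figure to reproduce: sample size, expected rates and interval width are blacked out, and no visible text names the interval method. The check is therefore whether each harm follows from the text. The numerical inputs below are all assumptions.

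**Step 1: what is checked, and is a repeat provided for?** In Section 7.6.3.1 the electrodes are those of the 12-lead reference; the watch is named separately. A check before they come off fits two stated needs: the interpretable reference ECG required for completion (7.5.4) and the exclusion of subjects whose reference waveform is unreadable (introduction to Section 8). A repeat prompted by a poor reference is not driven by the watch result. Section 3 describes what a user of the product is told, not a study step. Section 7.5.4 speaks of one measurement and does not require the watch to have classified it, so a Noise or Inconclusive result does not visibly prevent completion.

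**Step 2: interval width.** For *m* classified recordings per subject with intra-subject correlation ICC, the design effect is 1 + (m − 1) × ICC, and the true standard error is its square root times the binomial one.

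- Repeat only after failure, stop at the first classification: failed attempts are outside the accuracy set, so m ≤ 1 and the design effect is 1 + 0 × ICC = 1. Nothing is understated.
- m = 2, ICC = 0.3: 1 + 1 × 0.3 = 1.3; √1.3 = 1.14.
- m = 3, ICC = 0.7: 1 + 2 × 0.7 = 2.4; √2.4 = 1.55.

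The last two need planned replicates, or repeats of recordings that had already classified. In that case, simulation of a nominal 95% Clopper–Pearson interval (assumed sensitivity 0.95, 100 to 150 subjects, ICC 0.3 to 0.8, 20,000 runs) gives coverage of about 0.89 to 0.94 for m = 2 and 0.80 to 0.91 for m = 3. No visible text provides for either.

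**Step 3: failure rate.** Let p be the first-attempt failure rate and ρ the within-subject correlation, with one repeat after failure. The probability of two failures is p × (p + ρ(1 − p)). That is the reported rate if only the last attempt is kept. If every attempt is kept, the rate per measurement is (p + probability of two failures) / (1 + p).

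| p | ρ | Last attempt only | All attempts kept |
|---|---|---|---|
| 10% | 0 | 0.10 × 0.10 = 1.0% | 0.110 / 1.10 = 10.0% |
| 10% | 0.5 | 0.10 × 0.55 = 5.5% | 0.155 / 1.10 = 14.1% |
| 20% | 0 | 0.20 × 0.20 = 4.0% | 0.240 / 1.20 = 20.0% |
| 20% | 0.5 | 0.20 × 0.60 = 12.0% | 0.320 / 1.20 = 26.7% |

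The failure rate falls only under a last-attempt rule. Section 8 assigns an outcome to each measurement, and no visible sentence drops a failed one. With all attempts kept, the rate is unchanged or rises.

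**Step 4: heart rate.** The formulas in Section 8.3.1 also count measurements, but the visible criterion in 8.3.3 is a point limit of 5 bpm with no interval, so the interval argument does not apply there.

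**The case for a change.** The best case for a change is this. The word for recordings in Section 7.6.3.1 is plural and unqualified, and Section 3 uses the same term for the watch's own trace. The same section has subjects helped with the watch according to its user manual, so the product's advice to repeat could carry over into practice. The accuracy set in Section 8.1.1 shows no blackout, and it is where one would expect to read which attempt counts. It does not say, and gives no denominator for the failure rate. Even if all attempts were logged, second attempts selected because the first failed would enter sensitivity and specificity. With p = 10% and independent attempts, 0.10 × 0.90 = 0.09 of subjects would be classified at the second attempt, or 0.09 / 0.99 = 9.1% of classified recordings. A few sentences and an attempt counter on the case report form would settle it.

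The silence on repeats, analysed attempt and denominator stands. The rest is conditional on a repeat procedure that the visible text does not describe. The selection point has no established direction: late-classifying subjects may be harder to read, in which case including them would make accuracy look worse, not better. Nor can one say the plan lacks a rule: what enrolled subjects receive (7.1), parts of the measurement procedure (7.6.3.1) and the sample-size detail (8.1.2) are blacked out, and the workflow and schedule appendices are not shown.

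**Conclusion.** The concern does not hold as a defect. On the more natural reading, the on-site check protects the reference ECG, each subject provides one simultaneous measurement, and a one-sample binomial method suits that design. The interval harm does not follow from repeating after failure (design effect 1). The failure-rate harm needs a rule for discarding failed attempts that is not visible.

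What is left is missing detail that analysts would ordinarily fill in the obvious way: count the first watch recording that has a readable simultaneous reference, whatever its outcome, and report the failure rate over those recordings. The conclusion rests on one classified recording per subject, which the singular wording in Section 7.5.4 suggests but does not prove. If blacked-out text planned two or three recordings per subject, pooled as independent, standard errors would be understated by a factor of about 1.14 to 1.55 under the assumed correlations, and a clustered interval would be needed. The visible text gives no ground for assuming that.
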